All patients who had an attempted implant of the QuickFlex μ 1258T LV Lead will be included in the analysis of this endpoint. The survival time for all patients will be calculated as the number of days from implant or attempted implant to the date the complication was first discovered. For patients who do not experience a complication related to the LV lead at the time of their withdrawal, the survival time will be censored on the date of their withdrawal. For patients who have not experienced any complication related to the LV lead at the time of analysis, the survival time will be censored on the date of analysis. This analysis will also include all IDE study patients from sites that agree to participate in the PAS study. Patients from these sites who participated in the IDE study, but who do not consent to participate in the PAS study will be included in the analysis. If event free, they will be censored at the time of approval of the QuickFlex μ 1258T LV Lead or the last IDE follow-up visit (whichever is later). This will ensure that there is no bias in the estimates of complication rates; site selection criteria are independent of complication rates. The endpoint will be evaluated using the Kaplan-Meier method and the 95% lower confidence bound (LCB) will be obtained by transformation from its log scale, based on Peto et al². The null hypothesis will be rejected if the 95% LCB is greater than 92.5%. Kaplan-Meier curves will also be presented for each adverse event category of complication listed above.

A sub-group analysis will be performed to compare the LV lead related complication rates in patients rolled over from the IDE study to newly enrolled patients. Complication free survival estimates will also be estimated for the newly enrolled and IDE subjects by stratification in the Kaplan Meier analysis. The two groups will be compared using the log-rank test. As with the primary analysis, the sub-group analysis will include all IDE study patients from sites that agree to participate in the PAS study. Patients from these sites who participated in the IDE study, but who do not consent to participate in the PAS study will be included in the analysis. If event free, they will be censored at the time of approval of the QuickFlex μ 1258T LV Lead or the last IDE follow-up visit (whichever is later). This will ensure that there is no bias in the estimates of complication rates; site selection criteria are independent of complication rates.

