4.5.1 Enrollment Requirements

4.5.1.1 Enrollment

Patients will undergo screening evaluations as outlined by the inclusion/exclusion criteria. The proportion of male and female patients enrolled over time will be carefully monitored to ensure a representative sampling that is consistent with clinical practice. In both the SJM sponsored Post Approval Study, and the Attain Model 4193 LV lead study, male patients comprised 60%-70% of the study cohort. It is expected that the proportion of male patients in this study will be comparable.

Data will be collected on the patient's gender, age, ethnicity, tobacco use, cardiovascular history, arrhythmia history, NYHA functional classification, left ventricular ejection fraction, QRS duration, cardiomyopathy classification, and cardiac medications.

Patients who meet inclusion/exclusion criteria, sign an IRB/MEC approved informed consent, and have an implant or attempted implant of the QuickFlex® μ 1258T LV lead will be considered enrolled in the

study. The enrollment date for patients in the study will be the date of implant or attempted implant.

The IDE cohort patients will be eligible to rollover into the post approval study after signing consent for further data collection. The enrollment date for these patients will be the date of signing consent.

Complete and submit a Patient Status, Enrollment and Implant Case Report Form(s). If an adverse event or protocol deviation occurred during this visit, complete an Adverse Event and/or Deviation Case Report Form. Send the forms to St. Jude Medical, CRMD Sunnyvale, CA.

*Do not complete an Enrollment or Implant Case Report Form for the IDE rollover patients.

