6.0 Adverse Events

QuickFlex® μ 1258T Investigational Device Exemption (IDE) sites who agree to participate in the post approval study will be instructed to report all adverse events on IDE patients who are consented for participation in the post market study starting from the date of the last IDE follow up visit to ensure that all adverse events are reported. Adverse events will then continue to be reported every 6 months for the duration of the patient’s participation in the study.

Adverse events are any unfavorable clinical event which impacts, or has the potential to impact the health or safety of a patient caused by or associated with a study device or intervention. Adverse events will be classified as complication or observations.

Complications: Adverse events that require invasive intervention to resolve (e.g. lead dislodgment requiring repositioning).

Each complication will be reported in one of the following categories for analysis purposes:

- a) LV lead related complication: A complication that is related to the LV lead.
- b) Device related: A complication related to the device.
- c) Other system related complication: A complication that is related to the RV or RA lead.
- d) Procedure related complication: A complication related to an implant or system revision procedure.
- e) Other complication: Any complication that does not fall into one of the categories listed above.

Observations: Adverse events that can be managed without invasive intervention (e.g., oversensing or loss of pacing capture, which is remedied by reprogramming of the pulse generator). Observations will be reported in one of the following categories:

- a) LV lead related observation: An observation that is related to the LV lead
- b) Device related: An observation related to the device
- c) Other system related observation: An observation that is related to the RV or RA lead.
- d) Procedure related observation: An observation related to an implant or system revision procedure.
- e) Other observation: Any observation that does not fall into one of the categories listed above.

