- Pectoral/diaphragmatic/phrenic nerve stimulation
- Pericardial effusion
- Pericardial rub
- Pneumothorax/hemothorax
- Prolonged exposure to fluoroscopic radiation
- Pulmonary edema
- Renal failure from contrast media used to visualize coronary veins
- Rise in threshold and exit block
- Thrombolytic or air embolism
- Valve damage

Performance of a coronary sinus venogram is unique to lead placement in the cardiac venous system, and carries risks.

Potential complications reported with direct subclavian venipuncture include hemothorax, laceration of the subclavian artery, arteriovenous fistula, neural damage, thoracic duct injury, cannulation of other vessels, massive hemorrhage, and rarely, death.

Should an adverse event occur, complete an Adverse Event form and submit to St. Jude Medical. If an adverse event occurs between scheduled visits, the event should be reported at the next scheduled visit. Report the adverse event to the IRB/MEC per the IRB/MEC policy. Any explanted devices or leads should be returned to St. Jude Medical for analysis.

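### Event-free IDE patients who decline the post-approval study may be credited with unobserved time up to lead approval, so the no-bias statement is not supported for event ascertainment (conditional, small effect)

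*Protocol*

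**What the plan says.** Section 4.2.1 pools new patients with all IDE patients from participating sites in one Kaplan-Meier analysis. IDE patients are kept in even if they decline the new study: the text covers those who took part in the IDE study "but who do not consent to participate in the PAS study will be included in the analysis". Their censoring date is fixed, and the justification follows directly. Event-free patients are censored at lead approval "or the last IDE follow-up visit (whichever is later). This will ensure that there is no bias in the estimates of complication rates". The reason offered is that sites were chosen without regard to how often complications occurred.

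The same rule and the same assurance are repeated for the log-rank comparison of IDE with newly enrolled patients: "As with the primary analysis, the sub-group analysis will include all IDE study patients from sites that agree to participate in the PAS study".

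Data collection is described elsewhere. Section 4.5.1.1: "The IDE cohort patients will be eligible to rollover into the post approval study after signing consent for further data collection". Section 6.0 has IDE sites "report all adverse events on IDE patients who are consented for participation in the post market study starting from the date"; that starting point is each patient's final IDE visit, and the stated aim is that no adverse event goes unreported. Section 6.0 also says: "If an adverse event occurs between scheduled visits, the event should be reported at the next scheduled visit".

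**The concern.** The censoring rule and the reporting rule do not cover the same patients. If approval came after a patient's last IDE visit, a consenter's events in that interval are collected retrospectively under section 6.0. A non-consenter has no consent for further data collection and no next scheduled visit in this study, and the protocol names no other route by which a complication in that interval would become known. The patient nevertheless stays in the risk set until approval.

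Time at risk during which events cannot be seen lowers the estimated hazard. Complication-free survival can then only be overstated, which is the direction of the sponsor's desired outcome for a primary endpoint. The reason given for the absence of bias concerns how sites are chosen. It does not bear on whether events were ascertained in this interval.

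**Working it through.** The plan states no figure for this effect, so there is none to reproduce. The check is a bound under stated assumptions.

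**Inputs from the protocol**
- New patients: 1,884 enrolled, 1,036 evaluable (section 4.1).
- Total sample: 1,955 to 1,991 (section 4.1). Less 1,884, this leaves R = 71 to 107 IDE patients. Adjacent text is redacted, so reading these as consenting rollovers is an assumption.
- Null value: 92.5% at 5 years (section 4.2.1).

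**Assumptions (not in the protocol)**
- Non-consent p = 20% to 50%, in addition to R.
- A gap of 3 to 12 months between last IDE visit and approval, starting 9 to 12 months after implant.
- Constant hazards, true 5-year survival of 92.5%, and no gap events captured (worst case).

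**Formulas**
- Event hazard: -ln(0.925)/5 = 0.0156 per year.
- Attrition hazard in new patients: -ln(1036/1884)/5 = 0.1196 per year.
- Non-consenters: m = R·p/(1-p). Smallest 71 × 0.2/0.8 = 17.75; largest 107 × 0.5/0.5 = 107.
- Missed events: m × 0.0156 × gap.
- Shift in survival: 92.5 × [exp(∫ over the gap of 0.0156·m/(n(t)+m) dt) - 1] points, where n(t) = 1884·exp(-0.1196t) + R for the pooled analysis and n(t) = R for the IDE stratum.

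**Worst main case** (R = 107, m = 107, gap from year 1 to year 2)
- Missed events: 107 × 0.01559 × 1 = 1.67. Chance that none was missed: exp(-1.67) = 0.19.
- Pooled, at the gap midpoint: n(1.5) + m = 1,575 + 107 + 107 = 1,789. The integral is 0.01559 × 107/1,789 = 0.00093, so the shift is about +0.086 points.
- IDE stratum: 0.01559 × 107/214 = 0.0078, so the shift is +0.72 points.

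**Mildest main case** (R = 71, m = 17.75, gap of 0.25 year from 0.75 year)
- Missed events: 0.07. Chance that none was missed: 0.93.
- Pooled shift +0.004 points; IDE stratum +0.07 points.

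| | Shift (points) | Standard error (points) | Largest ratio |
|---|---|---|---|
| Pooled | +0.004 to +0.09 | 0.67-0.70 (Greenwood); 0.79 (Peto, 1,036 at risk) | 0.086/0.67 = 0.13; 0.086/0.79 = 0.11 |
| IDE stratum | +0.07 to +0.72 | 2.4-3.5 (Greenwood) | 0.72/2.42 = 0.30 |

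The Peto figure is 92.5 × √(0.075/1,036) = 0.79.

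**Sensitivity**
- If 71 to 107 is the whole IDE group, non-consenters included: pooled +0.003 to +0.05; IDE stratum shift unchanged, against a standard error of 2.8-4.8.
- Two-year gap with 50% non-consent on top of R: at most +0.18 pooled and +1.45 in the IDE stratum.
- IDE reporting continued to approval: zero. Last IDE visit after approval: zero.

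**The case against.** The strongest reply is that the interval lies before approval, when these patients came under the IDE protocol, which is not at hand. Sections 4.5.1.1 and 6.0 govern reporting in the new study and do not say that IDE reporting had stopped. Taking the later of two dates also makes sense only if some IDE visits could fall after approval, which hints that the IDE study may still have been running. This stands as a limit: no missed event is shown, and the effect may be zero. It does not remove the point. Section 6.0 starts the new reporting at the last IDE visit so that nothing is lost, which suggests, without proving, that capture under the IDE ended there.

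A second reply is that data sources are left to the statistical analysis plan. Here, however, the protocol itself fixes the censoring date and gives the assurance.

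A third is that the no-bias sentence is about selection. Read that way it is sound: keeping non-consenters in does guard against selection by consent. It is worded more broadly, about the estimates of complication rates as such.

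Two stronger readings are tempting. One is that the sentence is false and the primary result inflated. The documents do not support this, because they do not say when IDE reporting ended. The other is that non-consenters should be left out. That would bring back the selection problem which their inclusion addresses.

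**Conclusion.** The point holds as a low-severity, conditional one. For event-free non-consenters whose last IDE visit came before approval, the protocol fixes a censoring date beyond any event collection that it describes. Any resulting error favours the lead. Its size rests on assumed non-consent, gap length and IDE follow-up, and on no gap events being captured. On those terms it would not be expected to change the primary decision. In the IDE stratum it is relatively larger, at most about 0.3 of a standard error, but the log-rank comparison has no decision rule attached. The no-bias statement is unsupported as regards ascertainment; it is not shown to be wrong.

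**What to change.** In both places in section 4.2.1, for IDE patients who do not consent:

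- Count every LV lead complication recorded under IDE adverse-event reporting, including any recorded after the last visit. Do not cap counted events at a visit date, since that could discard a complication the IDE study itself documented.
- Censor event-free patients at the end of that ascertainment, set independently of events: the IDE exit or withdrawal date for those who left early, otherwise the last IDE follow-up visit at which adverse events were collected.
- Use the approval date only if IDE reporting continued to approval for that patient, and say so.
- List separately any complication that becomes known only after that reporting ended.
- Limit the no-bias sentence to selection of sites and patients.

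Patient-specific later contacts should not set the censoring date, because an event can prompt the contact. In simulation of the IDE stratum, with every gap event prompting a contact, that rule lowered the estimate by 0.09 to 1.40 points relative to censoring at the last IDE visit.

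The cost is a few sentences, using dates the IDE study should already hold. Credited follow-up falls by about 4 patient-years (17.75 × 0.25) to 107 patient-years (107 × 1). New patients contribute about 1,884 × (1 - 1036/1884)/0.1196 = 7,090 patient-years, and 107 rollovers followed for 5 years add 535. The loss is therefore at most about 107/7,625 = 1.4% under the main assumptions.

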4.2.2 Primary Endpoint 2 – LV Bipolar Capture Thresholds

LV lead bipolar pacing capture threshold at 5 years at 0.5 ms pulse width

The hypothesis is as follows:

[figure not shown]
H₀: Mean LV lead bipolar pacing capture threshold at 5 years \geq 3.5V

H₁: Mean LV lead bipolar pacing capture threshold at 5 years $<$ 3.5V

The objective performance criterion of 3.5V is based on an acceptable LV capture threshold of 3.5V.

The desired outcome is to reject the null hypothesis.

Sample Size

Patient Group

All patients who complete a 5 year follow-up and have a LV lead capture threshold at 0.5 ms pulse width will be included in the analysis.

Analysis

The sample average and sample standard deviation will be calculated for LV lead capture threshold. The 95% UCB for the mean LV lead capture threshold at 5 years at 0.5 ms pulse width will be calculated based on a t-distribution. The null hypothesis will be rejected if the 95% UCB is less than 3.5V. Summary statistics for LV lead bipolar capture thresholds will also be broken down and presented separately for the roll over and new enrolled patients.

³ Rhythm ICD/QuickSite Model 1056T Final Report. IDE G020114S/28.July 28, 2005

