3.0 Description of Device

In this study, the QuickFlex®µ 1258T LV Lead will be implanted with compatible legally marketed St. Jude Medical CRT-D devices.

The QuickFlex®µ 1258T left heart lead is a bipolar over-the-wire design, enabling implantation using either stylet or guidewire guided placement. The lead has an open lumen and an opening at the lead tip to allow the use of the guidewire. The lead body has Optim® (Elast-eon) insulation and a maximum lead body diameter of 4.7 Fr. Like the QuickSite® left heart lead family, the distal portion of the QuickFlex®µ 1258T left heart lead is pre-shaped in an “s-curve” configuration. The titanium nitride (TiN) coated platinum/iridium (PtIr) tip electrode contains a molded ring that elutes steroid. Additionally, the surface of the tip electrode is coated with a thin steroid film to provide immediate steroid release. A titanium nitride (TiN) coated platinum/iridium (PtIr) ring electrode is located 20 mm from the tip of the lead. The outer lead body is

¹ Heart disease and Stroke Statistics—2008 Update, American Heart Association

covered with Fast-Pass™ coating to increase lubricity during initial implant. The lead connector complies with the IS-1 connector standard ISO 5841-3.

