4.0 Clinical Protocol

4.1 Study Design and Scope

The QuickFlex®µ 1258T LV Lead study is a multi-center post-approval study that will be performed in compliance with the Conditions for Approval as agreed upon with the FDA. Patients may be enrolled in the study in one of two ways. Patients who previously participated in the QuickFlex®µ 1258T LV Lead IDE study and are at a center that is participating in the post approval study may be approached for enrollment into the post approval study. In addition, newly implanted patients will be approached at participating centers for participation in the study until the enrollment criteria is met. New patients who meet inclusion/exclusion criteria will have an attempted implant of the QuickFlex®µ 1258T lead. Patients who have an unsuccessful implant will be followed for 30 days for any adverse events and then withdrawn from the study, or may have an implant reattempted if the physician chooses to do so. Patients who have a successful implant of the LV lead will be considered to have received a successful CRT-D system. Following enrollment, patients will be followed at 6 months, and every 6 months thereafter, for 60 months of follow up (5 years). After patients complete 60 months of follow-up, their participation in the study will be terminated. There will be 1,884 new patients enrolled in the study to achieve an evaluable sample size of 1036 patients. In addition, every effort will be made to enroll existing IDE patients from sites participating in the Post Approval study. [REDACTED]

[REDACTED] for a total sample size of 1,955 to 1,991 patients. [REDACTED]

[REDACTED] If implantation rate at a study site is higher than the projected estimates, then the study enrollment period will be decreased proportionately. Reporting will occur per section 4.2.3 of the protocol. In order to accomplish this, the study will be conducted at a maximum of 80 study centers.

Definitions: The following definitions will be used in the QuickFlex®µ 1258T post approval study.

Abnormal Lead Pacing Impedance: Measured pacing impedances with values $\leq 200 \Omega$ or $\geq 2000 \Omega$

Adverse Event: Any unfavorable clinical event which impacts, or has the potential to impact the health or safety of a patient caused by or associated

with a study device or intervention. Adverse events are classified as complications or observations.

Cardiac Tamponade: Confirmed or suspected accumulation of fluid in the pericardial space.

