Loss of Capture: The inability of the device's output pulse to result in depolarization and contraction of the appropriate cardiac chamber. Causes include insufficient stimulus strength, separation of the electrode from the myocardium and placement of the stimulating electrode in contact with a non-responsive portion of the myocardium such as scar tissue.

Loss of Sensing: A condition in which the pulse generator is unable to sense intrinsic cardiac signals (applicable to RA and RV lead(s)).

Observation: Adverse events that can be managed without invasive intervention (e.g., over-sensing or loss of pacing capture, which is remedied by reprogramming of the pulse generator).

Over-sensing: The detection of inappropriate electrical signals by the pulse generator’s sense amplifier. These signals, such as myopotentials, electromagnetic interference, T waves or crosstalk between atrial and ventricular channels, must be of sufficient duration to interfere with normal device function. (applicable to RA and RV lead(s))

Pneumothorax: An accumulation or suspected accumulation of air in the pleural cavity.

[figure not shown]
Successful Implant: A SJM CRT-D system with an implanted QuickFlex®µ 1258T lead.

System Implant Attempt: A procedure in which a QuickFlex®µ 1258T lead implant is attempted.

Under-sensing: The failure of the pulse generator to sense P or R waves, causing delivery of inappropriately timed, asynchronous or competitive output pulses. Under-sensing can sometimes be corrected by programming the device to a more sensitive setting, i.e., decreasing the millivolt (mV) value (applicable to RA and RV lead(s)).

Unsuccessful Implant: An attempted implant that does not result in a successful QuickFlex®µ 1258T lead implant.

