4.2.1 Primary Endpoint 1 – Freedom from LV Lead-Related Complications

We will test the following hypothesis for LV lead related complication free survival at 5 years:

H_0 : Complication free survival at 5 years \leq 92.5%

H_1 : Complication free survival at 5 years $>$ 92.5%

The desired outcome is to reject the null hypothesis. The null hypothesis will be rejected at the 5% significance level if the 95% Lower Confidence Bound (LCB) for the freedom from complications is greater than 92.5%.

Sample Size

Analysis

All complications will be classified as related to the LV lead or as unrelated. The following complications will be included in the LV lead related analysis:

- Cardiac perforation
- Lead dislodgement that occurred greater than 30 days after implant
- Lead insulation damage
- Lead fracture
- Diaphragmatic/Phrenic nerve stimulation

- Abnormal LV lead performance (abnormal lead pacing impedance, elevated pacing thresholds, and loss of capture,)
- Other unexpected complications that are considered related to the LV lead

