4.5.2 System Revisions

For all system/lead revisions, complete the applicable testing as outlined in section 4.5.1.2. Any explanted devices or leads (including damaged leads, lead segments and lead fragments) should be returned to St. Jude Medical for analysis promptly. Any changes to the status of the lead (i.e., capped or removed) will be documented on the Product Out of Service Case Report Form. Complete an Adverse Event, System Revision, and Product Out of Service (if applicable) Case Report Forms. If an adverse event or protocol deviation occurred during the system revision procedure, complete an Adverse Event and/or Deviation Case Report Form. Send the forms to St. Jude Medical, CRMD Sunnyvale, CA.

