4.5.3 Follow-Up Requirements

Patients who have a successful system implant will be seen at 6 months after implant and every 6 months thereafter until the patient reaches the 5 year visit.

The schedule of follow-up visits is based on the date of successful LV lead implant for new patients and the date of signing consent for the IDE rollover patients. Table 4 outlines the time window that is permitted for each of the study interval visits.

Table 4: Study Interval Time Windows

6 months	Every 6 months thereafter until 5 years
± 45 days	± 60 days

4.5.3.1 6-Month Visit and Every 6 Months thereafter until 5 years

Perform a device follow-up and interrogate the device.

Perform the following electrical measurements: capture threshold testing for the LV lead using a pulse width of 0.5 ms and pacing lead impedance for the LV lead. All electrical measurements for the LV lead must be completed in the bipolar configuration.

**If final programming for LV pacing configuration is unipolar, perform electrical measurements (i.e. capture threshold test using a pulse width of 0.5ms and pacing lead impedance) in the selected unipolar vector.

***Note:** As referenced under the Definitions in section 4.1: Study Design and Scope, abnormal pacing lead impedances are defined as measured pacing impedances with values $\leq 200 \Omega$ or $\geq 2000 \Omega$. Pacing lead impedances measured up to 1999Ω are considered to be within the normal bounds of the performance of the LV lead because characteristics such as lead position, orientation of the electrodes, previous tissue injuries, etc., specific to each patient have been known to produce measured pacing impedances that are higher than anticipated. Should an LV lead pacing impedance be measured at $\leq 200 \Omega$ or $\geq 2000 \Omega$, exhibit increase or decrease of 25-30% in an acute setting, or between consecutive visits, the investigator should refer to the Users Manual, St. Jude Medical technical support or other St. Jude Medical clinical support personnel to diagnose potential lead failures.

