10.0 Withdrawals

Withdrawal is defined as termination of participation of a patient from a clinical trial. All reasonable efforts should be made to retain the subject in the clinical trial until completion of the clinical trial. Reasons for withdrawal include, but are not limited to the following:

- Heart Transplant
- Patient Death
- Patient and/or Family Request
- Patient Lost to Follow-Up - Defined as the following: Patient will be considered "lost to follow-up" after a minimum of two documented phone calls were made by personnel at the study center to the patient or emergency contact, a certified letter was sent to the last known address, and two consecutive visits pass without an investigator receiving data
- Patient Non-compliance
- Patient Participation terminated by Investigator
- Sponsor Request
- System explanted without a system replacement
- Unsuccessful Implant
- Removal of the QuickFlex® μ 1258T lead without a QuickFlex® μ 1258T lead replacement

Complete a Withdrawal Case Report Form and record all results. If the patient experienced an adverse event or protocol deviation, complete an Adverse Event and/or Deviation Case Report Form. Send the forms to St. Jude Medical, CRMD Sunnyvale, CA.

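### Primary Endpoint 2 averages only 5-year completers with a threshold value, so leads lost to threshold or capture failure drop out of the mean in the direction of success

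*Protocol*

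**What the plan says.** Protocol section 4.2.2 tests whether the mean bipolar capture threshold at 5 years, at 0.5 ms, is below 3.5 V. Success is declared if the t-based 95% upper confidence bound of the mean is under 3.5 V. The patient group is fixed in one sentence: "All patients who complete a 5 year follow-up and have a LV lead capture threshold at 0.5 ms pulse width will be included".

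Other sections decide who can have such a value:

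- Section 10.0 lists as a reason for withdrawal the removal of the 1258T lead when no other 1258T lead replaces it. A neighbouring entry is "System explanted without a system replacement". A patient who receives another 1258T lead is not withdrawn.
- Section 4.5.2 foresees leads taken out of service: "Any changes to the status of the lead (i.e., capped or removed) will be documented on the Product Out of Service Case Report Form".
- Section 4.5.3 requires bipolar measurement at every visit, and adds a unipolar one for some patients: "If final programming for LV pacing configuration is unipolar, perform electrical measurements". No visible text says what is recorded when a lead does not capture in bipolar mode.
- Section 4.2.1 counts as Endpoint 1 events complications of the type "Abnormal LV lead performance (abnormal lead pacing impedance, elevated pacing thresholds, and loss of capture", among all patients with an attempted implant.
- Section 4.1 limits complications to events needing invasive intervention. An observation is managed without it, and one example given is "loss of pacing capture, which is remedied by reprogramming of the pulse generator".

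**The concern.** Whether a lead has a 5-year value depends partly on the quantity being measured. Section 4.1 describes an elevated threshold at follow-up by reference to 3.5 V, the same figure as the performance criterion. Leads taken out of service for that reason, or for loss of capture, have high or unmeasurable thresholds. There are three routes by which the original lead's result is lost:

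1. The lead is removed or capped for threshold or capture failure, so no 5-year value exists.
2. The lead has no bipolar capture, so no bipolar value exists. This is an inference from the text, since the recording rule is not stated.
3. The lead is replaced by another 1258T lead. The patient stays in the study, and nothing in section 4.2.2 prevents the younger lead from supplying the 5-year value.

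Each route replaces a high value with nothing, or with a value from a different lead. A low mean is the desired result, so the omission favours success. It also flatters the reported 5-year mean, which is meant to describe chronic lead performance (section 2.0).

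**Working it through.** **What can be reproduced.** The sample size, expected mean and SD for Endpoint 2 are not visible, so there is no plan figure to reproduce for this endpoint. Section 4.1 gives only an overall figure: "There will be 1,884 new patients enrolled in the study to achieve an evaluable sample size of 1036 patients". That is 1,036/1,884 = 55.0% evaluable. It is not shown to be the Endpoint 2 sample size and is used here as a working value.

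**Assumptions (not in the documents).** n = 1,036 completers; SD s = 1.5 V; a failed lead scored at V = 5 V or 7.5 V; a one-sided 95% bound.

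**Effect on the mean.** If a share f of leads failed and the completers average m, the all-lead mean exceeds m by f × (V − m).

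| f | m = 2.0 V (V = 5 / 7.5) | m = 3.0 V (V = 5 / 7.5) |
|---|---|---|
| 1% | 0.030 / 0.055 V | 0.020 / 0.045 V |
| 2% | 0.060 / 0.110 V | 0.040 / 0.090 V |

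For a share of 1–2%, the understatement is therefore about 0.02–0.11 V.

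**Largest completer mean that passes under the present rule.** 3.5 − 1.646 × 1.5/√1,036 = 3.5 − 0.077 = 3.423 V.

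**Failures needed to reverse a success.** Add k leads scored at V to the n completers:

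- N = n + k
- M = (n·m + k·V)/N
- SD² = [(n − 1)s² + n(m − M)² + k(V − M)²]/(N − 1)
- bound = M + t(0.95, N − 1) × SD/√N

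The smallest k that brings the bound to 3.5 V or more, with its share k/N, is:

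| Completer mean | V = 5 V | V = 7.5 V |
|---|---|---|
| 3.25 V | 117 (10.1%) | 42 (3.9%) |
| 3.0 V | 284 (21.5%) | 103 (9.0%) |
| 2.0 V | 946 (47.7%) | 347 (25.1%) |

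One cell written out (m = 3.25, V = 7.5, k = 42): N = 1,078, M = (1,036 × 3.25 + 42 × 7.5)/1,078 = 3.416 V, SD = 1.685 V, bound = 3.416 + 1.646 × 1.685/√1,078 = 3.500 V.

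**Sensitivity to the SD.** With SD 1.0 V and 2.0 V, the counts at a completer mean of 3.25 V become 132 and 100 (V = 5 V), or 48 and 37 (V = 7.5 V). The picture does not change.

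**How far scoring could overshoot.** Withdrawn patients are not followed to 5 years. With about 55% expected to be evaluable, scoring every failure could count up to 1/0.55 = 1.8 times as many as would have reached the 5-year visit.

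**The case against.** The strongest reply is that the two primary endpoints divide the work: Endpoint 1 counts lead failures, and Endpoint 2 describes the electrical function of leads still in service. Much of this stands. Most failures treated invasively should be Endpoint 1 events, in a population of all attempted implants. Two gaps remain. Capture loss managed by reprogramming is an observation, so a lead without bipolar capture that is programmed to unipolar pacing could count in neither endpoint. And Endpoint 1 does not correct the mean that Endpoint 2 reports. Separately, section 4.2.4 lists loss of capture under both LV-lead-related and unrelated complications. Those passages must be reconciled, but this point does not depend on it.

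A second reply is that no consequence is shown, since every number beyond 3.5 V and 1,036 is assumed. That is correct. A reader might infer that the endpoint is likely to succeed falsely. The documents do not support that: they give no mean, SD or failure rate, and at a completer mean of 2.0 V no plausible failed share changes the verdict. A reader might also use Endpoint 1's 7.5% allowance as a ceiling on the failed share. It is not one. It is a Kaplan–Meier limit on a different population and set of events, and observations escape it. Nor are the 848 patients expected not to be evaluable (1,884 − 1,036) a pool of lead failures, because death, transplant and loss to follow-up are withdrawals too.

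Third, the patient-group sentence omits the word bipolar, and one might infer that unipolar values are admitted. The heading, the endpoint line and both hypotheses say bipolar, so this is a wording slip worth tidying and no more.

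Finally, making an assumed voltage score the primary analysis would change the estimand while keeping the 3.5 V criterion, and could over-count failures. That objection is accepted: the scored analysis belongs in a sensitivity role.

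**Conclusion.** The point holds as a matter of direction. Followed as written, section 4.2.2 omits or replaces the results of original leads that failed on threshold or capture, and this lowers the mean toward rejecting the null hypothesis. No visible text corrects it. The rule stands in the protocol itself, so it is not a detail left to the SAP.

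The size is unknown. Under the stated assumptions the reported mean is flattered by roughly a tenth of a volt or less when 1–2% of leads fail. The verdict is exposed only if the completer mean lies close to 3.5 V; well below that, the conclusion stands. The claim covers threshold and capture failures only. The effect of deaths, transplants, losses to follow-up and removals for other reasons, such as infection, is not known and is not part of it. Leads whose capture is kept at a higher output still have a value and remain in the mean.

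**What to change.** Amend section 4.2.2 in three places.

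1. State that the value is the bipolar threshold of the originally implanted 1258T lead, and that a value from a replacement lead does not count.
2. Keep the completer t-bound as the primary analysis. Add a pre-specified sensitivity (tipping-point) analysis that scores original leads without bipolar capture at 5 years, or removed, capped or replaced for threshold or capture failure, at one common upper voltage. Leads are "implanted with compatible legally marketed St. Jude Medical CRT-D devices", so one value should serve all models, and it should be fixed before 5-year data are reviewed. Deaths, transplants, losses to follow-up and removals for other reasons are not scored.
3. Report the number of such leads by reason, and read the two results as a bracket for this source of bias.

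No new data are needed: bipolar threshold printouts are exported at each visit (section 4.5.3.1), and changes in lead status go on the Product Out of Service form (section 4.5.2). The cost is protocol wording, a little more analysis and a slightly less favourable second figure. That figure is conservative, because withdrawn patients are not followed to 5 years. The study runs under conditions agreed with the FDA, so the wording change may need to be agreed there as well.
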